The aim of this study is to investigate the effects of combined tDCS and PC on recovery in master male runners following a 10K run. The study also aims to examine whether these interventions can shorten recovery time and prevent performance decline after prolonged and intense exercise.

This study will be conducted as a randomized, controlled, crossover trial using a mixed experimental design. Each participant will undergo four different recovery protocols in a randomized order, with a one-week interval between sessions. Randomization will be performed using Research Randomizer (<https://www.randomizer.org/>), assigning participants to one of four sequences (e.g., B–A–D–C). Participants will be identified only by numerical codes to ensure blinding and maintain confidentiality. Each participant will experience all protocols, allowing within-subject comparisons and minimizing order-related bias.

The four recovery protocols are:

- (A) tDCS group: transcranial direct current stimulation only
- (B) PC group: pneumatic compression only
- (C) tDCS + PC group: simultaneous application of both tDCS and PC
- (D) Control group: passive rest with no intervention

tDCS and PC interventions represent the independent variables, while dependent variables include WBQ, TQR, HRV, Stroop Test, vertical jump, and MVIC with EMG recordings.

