Participants will be 35 male long-distance master runners aged 40–55, residing in Bursa, Turkey, with at least five years of consistent training. They will train five days per week, 90 minutes per day, and must meet aerobic fitness criteria established by the American College of Sports Medicine, completing official 10K race under 50 minutes within last six months and maintain a weekly running volume of 60-80 km. Volunteers will be recruited from the local long-distance running community familiar to the principal investigator, [name]. Participants will be excluded if they have used regular medications within the last six months, consumed stimulants, caffeine, or alcohol within 24 hours prior to testing, smoke, have experienced musculoskeletal injuries in the past six months, are currently undergoing physical therapy, or have neurological conditions such as epilepsy or seizure history, or possess cardiac, brain, or other electronic implants. Additional exclusion criteria include open wounds or dermatological conditions on the head, circulatory disorders such as deep vein thrombosis, peripheral arterial disease, severe varicose veins, or prior exposure to tDCS or PC interventions. Participants may withdraw voluntarily, fail to attend sessions, or be removed if cardiovascular, neurological, or orthopedic complications occur during exercise or interventions, or if they experience excessive discomfort or adverse effects from the tDCS or PC procedures. Written informed consent will be obtained after explaining the study's purpose, procedures, potential risks, and benefits. Sample size was calculated using G*Power 3.1.9.7 for repeated measures ANOVA with within-between interaction, effect size $f = 0.30$, $\alpha = 0.05$, power = 0.80, resulting in $n = 28$. Accounting for potential dropouts, 35 participants will be recruited.

Screening and Familiarization Session:

Participants will undergo anthropometric measurements (weight, body fat, height) using Tanita BC 418 MA and Seca stadiometer. Physical fitness will be evaluated with a 12-minute Cooper Test on a 400 m track under controlled conditions (temperature 20–24°C, relative

humidity 50–70%, wind \leq 10 km/h). A 20-minute warm-up including jogging, accelerations, jumps, and stretching will precede testing. Distances will be recorded with a Polar V3 GPS watch.

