Participants will also complete a familiarization session with the 10K course, tDCS and PC devices, Stroop Test, MVIC, and vertical jump measurements to ensure procedural understanding.

Experimental Sessions

Pre-run Measurements (T1): Immediately prior to the 10K run, participants will complete the TQR, and the WBQ in the gym. Following this, the Polar Vantage V3 GPS-enabled watch and H10 heart rate strap will be fitted to each participant, and HRV data will be recorded for 5 minutes in a seated position.

After HRV recording, participants will perform the Stroop test under researcher supervision using a computer. Subsequently, vertical jump performance will be assessed. Participants will start from an upright standing position, perform a preliminary downward squat by flexing the knees and hips, and immediately extend the knees and hips to jump vertically. Vertical jump measurements will be performed three times with a 1-minute interval between trials, and the results will be recorded.

Following the jump assessment, participants will be fitted with an EMG device for the MVIC test. EMG signals will be recorded from the Vastus Lateralis, Rectus Femoris, and Vastus Medialis muscles during the test.

10K Run: After Test-1, participants will complete a 10K run on the athletics track at Bursa Uludağ University (BUU). The route begins and ends at the Faculty of Sports Sciences, BUÜ. Participants will have 30 minutes for individual warm-up and preparation.

The run will be performed at 75% intensity, determined using the Karvonen method, based on each participant's maximum heart rate obtained during an on-field Cooper test. Target heart rate zones will be set with a ± 5 bpm tolerance. GPS and HRV tracking will be conducted using the Polar Vantage V3 watch. Additionally, perceived exertion will be assessed verbally using the Borg-20 scale at the 5K mark and immediately after completing the run, with responses recorded by the researchers.

Post-run Measurements (T2): Immediately after completing the 10K run, the procedures conducted in Test 1 will be repeated.

Interventions:

Participants will be randomly assigned to one of four protocols:

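### The four crossover sequences are not fixed, nor required to balance periods or predecessors, and equal allocation is not stated, so the claim that order bias is minimised has no support in the text

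*Combined protocol and SAP*

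**What the plan says.** The design paragraphs under Method set out a four-period crossover: "Each participant will undergo four different recovery protocols in a randomized order", "with a one-week interval between sessions". On allocation they say "Randomization will be performed using Research Randomizer", "assigning participants to one of four sequences (e.g., B–A–D–C". No other sequence is printed. No Latin square, Williams design, counterbalancing, blocking or allocation ratio is named.

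The same paragraph gives its reason for expecting little order bias: "Each participant will experience all protocols, allowing within-subject comparisons and minimizing order-related bias".

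Under Experimental Sessions, the Interventions text describes the allocation differently: "Participants will be randomly assigned to one of four protocols". That is assignment to a protocol, not to a sequence.

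The Statistical Analysis section plans a Time by Group repeated-measures ANOVA with Bonferroni post-hoc tests. It names no period, sequence or carry-over term.

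**The concern.** Receiving all four conditions removes stable differences between runners. It does not deal with order. That depends on which four of the 24 possible orders are used and on how many runners follow each one. If conditions are spread unevenly over weeks, or one condition tends to follow another, part of a difference between conditions is a difference in week or in predecessor. The analysis has no term to correct for this, so any protection has to come from the sequence list, and the list is not given.

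The routes for order effects are plausible but not quantified. The Stroop, jump and maximal-contraction tests are repeated within and across four weekly sessions. Runners with earlier exposure to either intervention are excluded, although a familiarisation session introduces both devices. The control is rest without a device, so runners know which condition they are in. Well-being and recovery ratings at T3 could depend on what a runner received the week before, and that session's T1 need not absorb such an effect.

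**Working it through.** **The plan's own figure.** The plan gives no figure for order balance. Its only relevant number is the sample size, calculated "for repeated measures ANOVA with within-between interaction". With f = 0.30, alpha 0.05 and, as my assumptions, four groups, four measurements, correlation 0.5 and sphericity, lambda = f²Nm/(1 − rho) = 0.09 × 28 × 4/0.5 = 20.16 on 9 and 72 degrees of freedom. Power is 0.863 at N = 28 and 0.782 at N = 24, so 28 reproduces. Then 28/(1 − 0.20) = 35. Nothing in this calculation concerns sequences; only N = 35 is used below.

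**Which sets are possible.** Four distinct orders can be chosen in C(24,4) = 10,626 ways.
- 24 sets (0.23%) place each condition once in each period.
- 6 of these (0.06%) are Williams squares, where each condition also follows each other condition once.
- 6 sets tie every condition to a single predecessor.

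Among the C(23,3) = 1,771 sets that contain B-A-D-C, 4 balance periods. One of the 4 is a Williams square and one is the full rotation.

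| Set containing B-A-D-C | Sequences | Ordered pairs covered |
|---|---|---|
| Williams | B-A-D-C, A-C-B-D, C-D-A-B, D-B-C-A | 12 of 12 |
| Rotation | B-A-D-C, A-D-C-B, D-C-B-A, C-B-A-D | 4 of 12 |

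**Carry-over in the condition means (equal allocation, no adjustment).** Let c_X be the effect that condition X leaves on the next session's outcome.
- Rotation: A always follows B, D follows A, C follows D and B follows C, in three of four periods. The means of A, B, C and D carry 0.75c_B, 0.75c_C, 0.75c_D and 0.75c_A. For example, the bias in D − A is 0.75(c_A − c_B).
- Williams: each mean carries 0.25 of each of the other three, so the bias in X − Y is 0.25(c_Y − c_X).

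**Precision.** Variance of a pairwise contrast at 9/9/9/8, from a least-squares model with runner, period and condition effects, in units of sigma²/N:

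| Set | Without carry-over term | With carry-over term |
|---|---|---|
| Williams | 2.00 | 2.19 to 2.22 |
| Rotation | 2.00 | 10.7 to 11.3 |

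The ratio with the term is 10.7/2.2 = 4.9 to 11.3/2.2 = 5.1. Within the Williams square the term costs 2.2/2.0, about 10%.

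**Sequence sizes.** Assume each of 35 runners is allocated independently with probability 1/4 per sequence.
- The gap between largest and smallest sequence has median 6. P(gap ≥ 5) is 71% and P(gap ≥ 8) is 27%.
- The closest split, 9/9/9/8, has probability 4 × 35!/(9!·9!·9!·8!)/4^35 = 1.8%.

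In a period-balanced set, the weight of one period's effect in the contrast X − Y is the difference between two sequence sizes divided by N. A gap of 6 allows up to 6/35 = 17% of a period effect into a contrast when no period term is fitted; 9/9/9/8 allows at most 1/35 = 3%.

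**The case against.** **The rotation is hypothetical.** This stands. Nothing in the documents says the sequences are rotated. Among all possible sets the full rotation is as rare as the Williams square, 6 of 10,626 each, so 75% is a worst case and not an expectation. A reader might infer that each condition will follow the same predecessor throughout; the text only permits it.

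**Carry-over could still be adjusted for.** This also stands. A reader might infer that in the rotated set the effects of predecessor and current condition cannot be separated. They can, because period 1 has no predecessor and the model has full rank. The loss is one of precision.

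**The Williams square is not better for every contrast.** Correct. Suppose each active condition leaves the same effect c and rest leaves none. The rotation then gives zero bias in A − D and B − D (the H1 and H2 comparisons) and 0.75c in every contrast with C. The Williams square leaves 0.25c in each comparison with rest and none between active conditions. Under that assumption the gain is in H3 and in C against rest, not in H1 or H2.

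**Unblocked randomisation is not stated.** Correct. The protocol is silent, so the imbalance figures are conditional. A balanced list may already exist, in which case it needs only to be printed.

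**One week may be enough, and T1 is measured each session.** Partly stands. The interval may make physiological carry-over small, and an effect that shifts T1, T2 and T3 equally cancels from change within a session. Neither covers an effect on the change itself, such as a rating contrast at T3 or week-to-week change in response to the run.

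**The Interventions sentence can describe one session.** It can, and the design text makes the crossover clear. It is a wording conflict, not evidence of a parallel-group design.

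**Conclusion.** The point holds as a gap in the design. The sequence set and the allocation are left open, the reason given for low order bias does not follow, and the analysis has nothing to correct for order.

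Its size is bounded by what the text permits. In the worst set, 75% of one predecessor's carry-over falls on each condition mean, and carry-over adjustment has about five times the variance of the Williams square. Under unrestricted randomisation, a median sequence gap of 6 leaves condition partly mixed with period. These are shares of effects whose size the documents do not give.

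A reader might go further and infer that the trial's contrasts will be biased. The documents do not support that, because three sequences and the allocation method are undisclosed and any carry-over after one week is unknown. The change is worth making because it is nearly free before enrolment and cannot be repaired cheaply afterwards.

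**What to change.** Before enrolment:

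1. Print the four sequences as the one Williams square that contains the protocol's example: B-A-D-C, A-C-B-D, C-D-A-B, D-B-C-A.
2. Randomise runners to sequence in permuted blocks of 4 or 8. With 35 runners, blocks of 4 give eight full blocks plus three runners, so 9/9/9/8. Blocks of 8 give that or 10/9/8/8. At 28 completers an exact 7/7/7/7 is possible, but dropout may upset it.
3. Add a period term to the analysis. If the Time by Group layout is kept, include period by time, because conditions are compared on change within a session.
4. Reword the Interventions sentence so that each session's protocol is the one due that week in the runner's assigned sequence, and base the order-bias statement on the balanced sequences.

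The Williams square reduces unadjusted carry-over bias but does not remove it: 25% of the difference between the two compared conditions' carry-overs remains. A carry-over term can be fitted as a sensitivity analysis.

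The cost is a revised randomisation list and a few sentences of text. There are no added runners or sessions and no loss of precision without a carry-over term. Fitting that term adds about 10% to contrast variance.

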Study Protocol and Statistical Analysis Plan

Title: The Effects of Combined Transcranial Direct Current Stimulation and Pneumatic Compression on Selected Recovery Parameters After a 10K Run

NCT Number: Pending

Ethics Committee Approval Number: 2025-17/11

Date: 16 December 2025

Objectives and Hypotheses

Research Question:

In this context, the primary research question is:

"How do transcranial direct current stimulation (tDCS), pneumatic compression (PC), and their combined application affect subjective well-being, total quality of recovery (TQR), heart rate variability (HRV), neuromuscular performance (maximal voluntary isometric contraction and vertical jump), and cognitive function (Stroop Test) in master male long-distance runners aged 40–55, immediately before, immediately after a 10-kilometer (10K) run, and following a 20-minute recovery intervention?"

Hypotheses:

- **H1:** tDCS application will significantly improve post-run recovery markers, including subjective well-being, TQR, HRV, neuromuscular performance, and cognitive function.
- **H2:** PC application will significantly improve post-run recovery markers, including subjective well-being, TQR, HRV, neuromuscular performance, and cognitive function.
- **H3:** Combined application of tDCS and PC will produce greater improvements in recovery markers compared to either intervention applied individually.

Objective:

The aim of this study is to evaluate the effects of tDCS, PC, and their combined application on physical, physiological, psychological, and cognitive recovery in master male long-distance runners after a 10K run, with the goal of shortening recovery time and preventing performance decline following intensive exercise.

Specific Aims:

- To investigate the effects of tDCS and PC and combined tDCS+PC on post-run muscle fatigue and neuromuscular performance (maximal voluntary isometric contraction and vertical jump).
- To examine changes in subjective well-being and TQR as indicators of psychological recovery.
- To assess cognitive recovery using the Stroop test.
- To analyze physiological responses by evaluating HRV following each intervention.
- To compare the individual and combined contributions of tDCS and PC to overall recovery.

Method

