- **(D) Control:** Participants in the control group will be positioned in a semi-recumbent posture at approximately 45° recline for 20 minutes without receiving any intervention. During this period, participants will remain passive in a quiet, distraction-free environment. The 45° semi-recumbent posture is consistent with the intervention groups to control for physiological variations arising from body positioning (e.g., blood flow, venous return, postural hemodynamic changes). Active recovery strategies (e.g., walking, stretching) were deliberately excluded to avoid potential confounding effects. This standardized passive rest condition allows for a valid comparison of intervention effects between groups.

Post-intervention Measurements (T3): The procedures conducted in Test 1 will be repeated immediately after the participant completes the assigned intervention protocol.

Outcome Measures:

- Subjective scales: Well-being Questionnaire, Total Quality Recovery
- Heart rate variability (HRV) and GPS
- Cognitive performance via Stroop Test
- Vertical jump height via My Jump app
- MVIC with EMG on quadriceps muscles following SENIAM protocol
- tDCS and PC applied according to standardized protocols

Statistical Analysis

Data will be analyzed with IBM SPSS 29. Normality (Shapiro-Wilk), homogeneity (Levene), and sphericity (Mauchly) will be tested. Two-way repeated measures ANOVA (4 Time \times 4 Group) will assess interactions, with Bonferroni post-hoc tests. Effect sizes will be reported using partial eta squared (η_p^2): small (>0.01), medium (>0.06), large (>0.14). Significance threshold $p < 0.05$.

This study will provide comprehensive insight into the effects of tDCS and PC, alone and in combination, on recovery in older endurance athletes, contributing evidence-based recommendations for optimizing performance and minimizing injury risk.

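### No primary outcome is named among at least six of equal rank, error across their interaction tests is not controlled, and no rule says how many must be positive to support H1-H3

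*Combined protocol and SAP*

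**What the plan says.** The design paragraphs under Method give the outcome list: "dependent variables include WBQ, TQR, HRV, Stroop Test, vertical jump, and MVIC with EMG recordings". The wording leaves the list open-ended. The Outcome Measures section repeats the outcomes without separating primary from secondary.

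The word primary is attached only to a question (Research Question: "In this context, the primary research question is"). That question asks how the interventions "affect subjective well-being, total quality of recovery (TQR), heart rate variability (HRV), neuromuscular performance" and cognitive function.

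Under Hypotheses, H1 reads "tDCS application will significantly improve post-run recovery markers, including subjective well-being, TQR, HRV, neuromuscular performance, and cognitive function". H2 has the same form for pneumatic compression (PC). H3 expects "greater improvements in recovery markers compared to either intervention applied individually" and names no marker.

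The sample-size statement, in the participant paragraph under Method, uses "repeated measures ANOVA with within-between interaction, effect size $f = 0.30", alpha 0.05 and power 0.80, giving n = 28, with 35 to be recruited. It names no outcome.

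Statistical Analysis specifies one two-way repeated measures ANOVA, which "will assess interactions, with Bonferroni post-hoc tests", at a 0.05 threshold. Within the MVIC outcome, Pre-run Measurements (T1) adds that "EMG signals will be recorded from the Vastus Lateralis, Rectus Femoris, and Vastus Medialis muscles during the test".

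**The concern.** Four things are left open: which outcome decides each hypothesis, how many outcomes must be significant, which time contrast counts, and which condition pairs form the Bonferroni family. The number of variables is open too, since three EMG channels sit inside one listed outcome and no HRV or Stroop index is specified.

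This has two consequences. First, the plan followed as written runs at least six interaction tests, each at 0.05, with nothing linking them. Second, a statement that H1 is supported could mean that one marker passed or that all did. Those standards have very different false-positive rates and very different power, and a reader could not tell which was applied. Nothing prevents the choice from being made after the data are seen.

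**Working it through.** **1. The plan's own figure.** The inputs f = 0.30, alpha = 0.05 and power = 0.80 are stated. The number of groups k, measurements m, correlation rho and epsilon are not. I took k = 4 and m = 4 from the stated 4 × 4 model and assumed rho = 0.5 and epsilon = 1. For the within-between interaction:

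- lambda = f² × N × m / (1 − rho), df1 = (k − 1)(m − 1), df2 = (N − k)(m − 1).
- N = 28, m = 4: lambda = 0.09 × 28 × 4 / 0.5 = 20.16, df = 9 and 72, power 0.863.
- The smallest N reaching 0.80 is 25, or 28 in four equal groups, so n = 28 is reproduced under these settings. The calculation covers one interaction test at 0.05, for an unnamed outcome.

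**2. Interaction tests, no true effects.** With K independent tests at 0.05, the chance of at least one false positive is 1 − 0.95^K.

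- K = 6: 1 − 0.95^6 = 26.5%.
- K = 9 (MVIC force and three EMG channels counted separately, so 6 + 3): 1 − 0.95^9 = 37.0%.

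The outcomes are probably correlated, and the documents give no correlations. Simulation with 28 completers, four conditions, the three scheduled time points and six outcomes gives 26.7%, 25.0%, 22.7% and 15.6% at common correlations 0, 0.3, 0.5 and 0.8.

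**3. Hypothesis level, no true effects.** The same simulation needs further assumptions, because the plan fixes none of these points: contrasts on the T2-to-T3 change, two-sided Bonferroni over all six condition pairs (0.05 / 6 = 0.0083), and any one of six outcomes sufficing. H1 is A vs D, H2 is B vs D, and H3 is C vs A and C vs B. Because H1-H3 claim improvement, only results in that direction count. Ranges run over correlations 0.8 to 0.

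| Reading | False support for any of H1-H3 |
|---|---|
| One H3 contrast is enough | about 6-9% |
| Both H3 contrasts needed | about 3-5% |
| Both needed, and contrasts only after a significant interaction | about 1.5-2.5% |
| Every marker must improve | near zero (0.1% or less) |

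The first three rows rise if more than six variables are tested.

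**4. Price of the strictest reading.** If all six interactions had to be significant, at 0.863 power each and independence, joint power would be 0.863^6 = 41%. The permissive and strict readings therefore describe two very different trials.

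**The case against.** The strongest reply is that Bonferroni is in the plan, the outcomes are listed in advance with one model for all, and reporting marker by marker is ordinary practice. Much of this stands at hypothesis level. Within-outcome Bonferroni, the direction built into H1-H3, and the usual practice of following up only significant interactions bring false support to 5% or less on the readings where H3 needs both contrasts. It does not answer the interaction level: post-hoc Bonferroni adjusts comparisons within an outcome and does nothing across outcomes.

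A second reply is that H1 and H2 join their markers with an *and*, so all must improve. If so, error is not inflated. But the plan states no such rule, and H3 names no markers at all.

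A reader might infer that the trial has a 26% chance, or about 17%, of falsely supporting a hypothesis. The documents support neither. The 26% concerns interaction tests. About 17% arises only if significant worsening counts as support, one H3 contrast suffices and the interaction is ignored; even then it is no ceiling, since nine outcomes counted that way give about 24%. A reader might also infer an intention to choose the outcome afterwards. Nothing in the text shows that; it is a risk left by the missing rule.

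**Conclusion.** The concern holds in a limited form. No outcome is primary, the sample size belongs to none, and error across the interaction tests is not controlled: 26.5% for six independent tests, about 15-25% at correlations 0.8 to 0.3, and 37% for nine independent tests. At hypothesis level the inflation is modest at most, about 6-9% on the most permissive reading in the table and 5% or less on the others. It would be wrong to conclude that H1-H3 have no multiplicity protection.

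The main defect is that the plan does not say which reading applies, so the meaning of a positive H1, H2 or H3 is not fixed in advance. That conclusion needs no simulation. The percentages rest on an assumed common correlation, 28 completers, and, at hypothesis level, the assumed contrast and six-pair family. The change should be made, and it needs no new data.

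**What to change.** Choose one of the following before outcome data are seen.

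**Option 1: one primary outcome.** Name it and its deciding time contrast, and tie the sample-size statement to that test. Test its interaction at 0.05. Then decide H1 (A vs D), H2 (B vs D) and H3 (C vs A and C vs B, both required) by Bonferroni contrasts on that outcome, in the direction of improvement. State the family: all six pairs (0.05 / 6 = 0.0083) or the four hypothesis pairs (0.05 / 4 = 0.0125). The other outcomes are secondary and supportive only, with Holm across their interaction tests; they do not decide H1-H3.

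*Cost:* H1-H3 then rest on one marker, which narrows a question written across several domains. The choice of time points also affects power. With f = 0.30 held and k = 4, rho = 0.5, epsilon = 1 assumed, power at n = 28 is 0.86 with four times (lambda 20.16), 0.79 with three (lambda 15.12) and 0.69 with T2 and T3 alone (lambda 10.08). Either keep the interaction over all scheduled times as the gate, or restate the power.

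**Option 2: six co-equal outcomes.** This keeps the multi-domain question. Apply Holm across the six interaction tests (first step 0.05 / 6 = 0.0083) and state how many must pass to support each hypothesis.

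*Cost:* under the same assumptions, power at 0.0083 is about 0.52 (three times) to 0.64 (four times) at n = 28, and 0.70 to 0.81 if all 35 complete.

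Under either option, label the EMG channels and any extra HRV or Stroop indices exploratory.

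### A runner who tolerates a device poorly may be removed from the whole study, with no measurement planned after a stop, so the device-versus-rest comparisons may describe only the runners retained (minor; cheap to improve)

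*Combined protocol and SAP*

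**What the plan says.** All references are to the combined protocol and SAP.

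- **Method, participants.** One sentence lists the routes out of the study. It begins: "Participants may withdraw voluntarily, fail to attend sessions, or be removed if cardiovascular, neurological, or orthopedic complications occur". Poor tolerance of a device is a separate ground at its end: "or if they experience excessive discomfort or adverse effects from the tDCS or PC procedures". What is removed is the participant, not the session. The wording permits removal; it does not require it.
- **Post-intervention Measurements (T3).** The Test 1 procedures "will be repeated immediately after the participant completes the assigned intervention protocol". Nothing is said about T3 after an early stop.
- **Method, design.** Four conditions are planned for every runner: "Each participant will experience all protocols, allowing within-subject comparisons and minimizing order-related bias". tDCS is used in A and C, PC in B and C, and neither in D.
- **Statistical Analysis.** The method is a "Two-way repeated measures ANOVA". No analysis set, missing-data rule or sensitivity analysis is given.
- **Sample size.** The only response to loss is over-recruitment: "Accounting for potential dropouts, 35 participants will be recruited", against a calculated 28.
- **Objective, H1 and H2.** These are worded for male master runners and for applying tDCS or PC, with no restriction to runners who tolerate the device. Tolerability is not among the listed outcomes.

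**The concern.** Retention can depend on the response to the treatment under test. The crossover compares each retained runner with himself, but that does not help if who is retained depends on how he reacted to a device.

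Two things are at stake. First, the estimated effect of tDCS or PC against rest may apply to a narrower group than the one in the objective. WBQ and TQR are reports of how the runner feels, so a runner who found a device unpleasant might plausibly have scored low after it, and losing him would flatter the device. Second, the loss is larger than it needs to be. A runner who cannot tolerate tDCS could usually still do rest and PC alone, and one who cannot tolerate PC could still do rest and tDCS alone. Over-recruitment protects power but does not correct who is left.

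**Working it through.** **The plan's own figures.** With 4 groups, 4 measurements, a within-runner correlation of 0.5 and sphericity (none of these inputs is stated beside the calculation), the within-between interaction at f = 0.30, alpha 0.05 and power 0.80 needs N = 25. Rounded up to a multiple of 4 this is 28, as stated. Then 28 / (1 − 0.20) = 35, so the implied allowance is 20%, or 35 − 28 = 7 runners. Those 7 also cover withdrawal, non-attendance and complications during exercise, and are shared by two devices. They are not an estimate of device intolerance.

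**Selection shift.** The documents give no stop rate and no link between tolerability and outcome, so both are assumed. Let m of 35 runners be removed for one device, these being the m lowest on tolerability. Let ρ be the correlation between tolerability and the runner-level device-minus-rest difference, whose SD is set to 1.

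Shift = ρ × mean of the retained 35 − m standard normal values; SE = 1/√(35 − m).

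| m | retained mean | shift, ρ = 0.3 | shift, ρ = 0.5 | SE | shift / SE |
|---|---|---|---|---|---|
| 1 | 0.0620 | 0.019 | 0.031 | 0.171 | 0.11–0.18 |
| 2 | 0.1150 | 0.035 | 0.058 | 0.174 | 0.20–0.33 |
| 3 | 0.1638 | 0.049 | 0.082 | 0.177 | 0.28–0.46 |

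With ρ = 0 or m = 0 the shift is zero.

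**Sessions lost.** There are 35 × 4 = 140 sessions. Complete-case analysis loses 4m, that is 4, 8 or 12. If only the other session with the poorly tolerated device is withheld, the loss is m, that is 1, 2 or 3.

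**What the fix recovers.** This was simulated for tDCS minus rest at T3 only. Assumptions: four balanced sequences; the stop comes at the runner's first tDCS session; under the fix T3 is taken there, rest and PC go ahead and the other tDCS session is withheld; the model has condition, period and random runner. Bias in SD, with intolerance affecting A and C alike:

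| ρ, m | complete case | mixed model, runner still removed | mixed model with the fix |
|---|---|---|---|
| 0.3, 1 | 0.020 | 0.019 | 0.006 |
| 0.3, 3 | 0.049 | 0.048 | 0.016 |
| 0.5, 1 | 0.031 | 0.030 | 0.011 |
| 0.5, 3 | 0.081 | 0.078 | 0.026 |

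At ρ = 0.5 the reduction is 1 − 0.011/0.031 = 65% for one stop and 1 − 0.026/0.081 = 68% for three. A repeat simulation gave about 60%. If intolerance affects A alone, the fix takes 0.031 to 0.016 (one stop) and 0.085 to 0.040 (three stops), about half. The gain comes from continued measurement; changing the model alone gains almost nothing.

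**Dilution.** If the full effect is 0.5 SD and half of it is obtained in a stopped session, the partial sessions lower the estimate by 0.005, 0.009 or 0.013 SD for 1, 2 or 3 stops.

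**The case against.** The strongest reply is that the chain is conditional and the numbers are small. Some runner must react badly, the investigator must choose to remove him under a permissive rule, and the analysis must then discard him. No section states the last step, says that collected data are thrown away, or forbids T3 after a stop. Contraindications are screened out, and "Participants will also complete a familiarization session with the 10K course, tDCS and PC devices" before the trial sessions, which points to few stops. Converted to a two-sided 5% test, one removal gives a false-positive rate of about 5.1 to 5.4% and three give about 5.9 to 7.5%. Even that supposes the removed runners are strictly the least tolerant. All of this stands, and it is why the priority is minor.

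A second reply is that the effect of a full 20-minute application is a legitimate target for a small crossover. That also stands, but it does not require removing the runner: a full-dose completers' analysis remains available under the fix.

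A third is that continuing after an adverse effect raises safety questions, including which device caused a stop in session C. This is fair, so those decisions are given to the investigator below.

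A reader might infer that H1 and H2 will necessarily describe only tolerators, or that the devices will look better than they are. The documents support neither. The first needs all three steps above. The second needs a link between discomfort and outcome that the documents do not give.

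**Conclusion.** The gap is real, and it is conditional. The plan allows whole-study removal because of the response to a device and provides no measurement after a stop. If removal happens and complete cases are analysed, the device-versus-rest comparisons describe the retained runners, and 4 sessions are lost per removed runner where 1 would often do.

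The shift is roughly 0.02 to 0.08 SD for 1 to 3 removals per device, under an assumed correlation of 0.3 to 0.5, with screening and familiarization pointing to the low end. A shift favouring the devices on WBQ and TQR is plausible but unproven. For HRV, Stroop, jump, MVIC and H3 the direction is undetermined. Priority is minor. The reason to act is that the change is cheap, keeps every safety stop and must be made in advance, since T3 data not taken after a stop cannot be recovered later.

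**What to change.** Amend the removal rule along these lines:

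- Stopping a device for discomfort or an adverse effect ends that device session, and later sessions with that device if the investigator judges them unsafe. It does not by itself remove the participant. The right to withdraw is unchanged, and all data collected are kept.
- After a stop, the runner stays semi-recumbent to the end of the 20 minutes, matching the control condition ("semi-recumbent posture at approximately 45° recline for 20 minutes without receiving any intervention"). The T3 questionnaires are then taken, with the other T3 tests if the investigator judges them safe, and the session is flagged.
- If a stop in session C cannot be attributed to one device, the investigator decides whether to withhold later sessions with either.
- Rest and tolerated-device sessions go ahead unless the investigator judges further runs unsafe or the runner withdraws.

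Analyse all available sessions by assigned condition with a linear mixed model (fixed condition, time, condition-by-time and period; random runner). Give full-dose completers as a sensitivity analysis, and report stops and adverse effects by condition.

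The cost is a short protocol amendment, a change of planned analysis and a simple stop log. The downside is slight dilution (0.005 to 0.013 SD under the assumptions above), and jump or MVIC may still be missing after a stop. The selection falls by roughly half to two-thirds, as simulated for tDCS minus rest only; it is not removed.
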